## — LIST EACH DEVICE BEING TESTED IN STUDY IN THE SPACE BELOW —

Device Name:

Is the study being conducted under a valid Investigational Device Exemption (IDE),  
Humanitarian Device Exemption (HDE) or Compassionate Use?

Yes  No

If Yes, complete the following:

IDE or HDE #(s)

IDE/HDE Submitted/Held by:

Sponsor:

Held By:

Investigator:

Held By:

Other:

Held By:

Check if this is a Treatment IDE or Compassionate Use under the Food and Drug Administration (FDA) Expanded Access program.

For Individual or Small Group Expanded Access, see [FDA's Early Expanded Access Program Information](#), and attach the following:

- FDA expanded access approval or sponsor's authorization;
- An independent assessment from an uninvolved physician, if available;
- Confirmation of agreement from manufacturer or entity authorized to provide access to the product.

For guidance and reporting requirements at the conclusion of treatment see the [Medical Device SOP](#).

Does the intended use of any research device being tested (not clinically observed) in this study meet the regulatory [definition](#) of Significant Risk (SR) device?

- Yes. Device(s) being tested in this study presents a potential for serious risk to the health, safety, or welfare of a subject and (1) is intended as an implant; or (2) is used in supporting or sustaining human life; or (3) is of substantial importance in diagnosing, curing, mitigating or treating disease, or otherwise prevents impairment of human health; or (4) otherwise presents a potential for serious risk to the health, safety, or welfare of a subject.
- No. All devices being tested in this study do not present a potential for serious risk to the health, safety, or welfare of subjects/participants.

Complete and attach the required [Study Device Form](#), picking the "Study Device Form" for the document type. Any applicable device documentation (e.g., Manufacturer information; patient information packet; approved labeling; FDA correspondence, etc.) should be attached using "Other Device Documentation" for the document type.

Attachments

## RESEARCH SITES

0 unresolved  
comment(s)

To complete this section, ensure the responses are accurate then click "SAVE".

A) Check all the applicable sites listed below at which the research will be conducted. If none apply, you do not need to check any boxes.

## UK Sites

- UK Classroom(s)/Lab(s)
- UK Clinics in Lexington
- UK Clinics outside of Lexington
- UK Healthcare Good Samaritan Hospital
- UK Hospital

## Schools/Education Institutions

- Fayette Co. School Systems \*
- Other State/Regional School Systems
- Institutions of Higher Education (other than UK)

**\*Fayette Co. School systems, as well as other non-UK sites, have additional requirements that must be addressed. See ORI's [IRB Application Instructions - Off-site Research](#) web page for details.**

## RESEARCH ATTRIBUTES

0 unresolved  
comment(s)

Indicate the items below that apply to your research. Depending on the items applicable to your research, you may be required to complete additional forms or meet additional requirements. Contact the ORI [contact]) if you have questions about additional requirements.

Not applicable

Check All That Apply

- Academic Degree/Required Research
- Alcohol/Drug/Substance Abuse Research
- Biological Specimen Bank Creation (for sharing)
- Cancer Research
- CCTS-Center for Clinical & Translational Science
- Certificate of Confidentiality
- Clinical Research
- Clinical Trial - Phase 1
- Clinical Trial
- Collection of Biological Specimens for internal banking and use (not sharing)
- Community-Based Participatory Research
- Deception
- Educational/Student Records (e.g., GPA, test scores)
- Emergency Use (Single Patient)
- Gene Transfer
- Genetic Research
- GWAS (Genome-Wide Association Study) or NIH Genomic Data Sharing (GDS)
- Human Cells, Tissues, and Cellular and Tissue Based Products
- Individual Expanded Access or Compassionate Use
- International Research
- Planned Emergency Research Involving Exception from Informed Consent
- Recombinant DNA
- Registry or data repository creation
- Stem Cell Research
- Suicide Ideation or Behavior Research
- Survey Research
- Transplants
- Use, storage and disposal of radioactive material and radiation producing devices
- Vaccine Trials

For additional requirements and information:

- [Cancer Research \(MCC PRMC\)](#)
- [Certificate of Confidentiality](#) (look up "Confidentiality/Privacy...")
- [CCTS \(Center for Clinical and Translational Science\)](#)
- [Clinical Research](#) (look up "What is the definition of....")
- [Clinical Trial](#)
- [Collection of Biological Specimens for Banking](#) (look up "Specimen/Tissue Collection...")
- [Collection of Biological Specimens](#) (look up "Specimen/Tissue Collection...")
- [Community-Based Participatory Research](#) (look up "Community-Engaged...")
- [Data & Safety Monitoring Board \(DSMB\)](#)

\*For Medical IRB: [Service Request Form](#) for CCTS DSMB

- [Data & Safety Monitoring Plan](#)
- [Deception\\*](#)

\*For deception research, also go to the E-IRB Application Informed Consent section, checkmark and complete "Request for Waiver of Informed Consent Process"

- [Emergency Use \(Single Patient\) \[attach Emergency Use Checklist\] \(PDF\)](#)
- [Genetic Research](#) (look up "Specimen/Tissue Collection...")
- [Gene Transfer](#)
- [HIV/AIDS Research](#) (look up "Reportable Diseases/Conditions")
- [Screening for Reportable Diseases \[E2.0000\] \(PDF\)](#)
- [International Research](#) (look up "International & Non-English Speaking")
- [NIH Genomic Data Sharing \(GDS\) Policy \(PDF\)](#)
- [Planned Emergency Research Involving Waiver of Informed Consent\\*](#)

\*For Planned Emergency Research Involving Waiver of Informed Consent, also go to the E-IRB Application Informed Consent section, checkmark and complete "Request for Waiver of Informed Consent Process"

- [Use, storage and disposal of radioactive material and radiation producing devices](#)

## FUNDING/SUPPORT

0 unresolved  
comment(s)

If the research is being submitted to, supported by, or conducted in cooperation with an external or internal agency or funding program, indicate below all the categories that apply. [?](#)

Not applicable

## Check All That Apply

- Grant application pending
- (HHS) Dept. of Health & Human Services
  - (NIH) National Institutes of Health
  - (CDC) Centers for Disease Control & Prevention
  - (HRSA) Health Resources and Services Administration
    - (SAMHSA) Substance Abuse and Mental Health Services Administration
  - (DoJ) Department of Justice or Bureau of Prisons
  - (DoE) Department of Energy
  - (EPA) Environmental Protection Agency
- Federal Agencies Other Than Those Listed Here
- Industry (Other than Pharmaceutical Companies)
- Internal Grant Program w/ proposal
- Internal Grant Program w/o proposal
- National Science Foundation
- Other Institutions of Higher Education
- Pharmaceutical Company
- Private Foundation/Association
- U.S. Department of Education
- State

Other:

Patient Centered Outcomes Research Institute (PCORI)

Click applicable listing(s) for additional requirements and information:

- [\(HHS\) Dept. of Health & Human Services](#)
- [\(NIH\) National Institutes of Health](#)
- [\(CDC\) Centers for Disease Control & Prevention](#)
- [\(HRSA\) Health Resources & Services Administration](#)
- [\(SAMHSA\) Substance Abuse & Mental Health Services Administration](#)
- Industry (Other than Pharmaceutical Companies) [[IRB Fee Info](#)]
- [National Science Foundation](#)
- [\(DoEd\) U.S. Department of Education](#)
- [\(DoJ\) Department of Justice or Bureau of Prisons](#)
- [\(DoE\) Department of Energy Summary](#) and [Department of Energy Identifiable Information Compliance Checklist](#)
- [\(EPA\) Environmental Protection Agency](#)

## Add Related Grants

If applicable, please search for and select the OSPA Account number or Electronic Internal Approval Form (eIAF) # (notif #) associated with this IRB application using the "Add Related Grants" button.  
If required by your funding agency, upload your grant using the "Grant/Contract Attachments" button.

[Add Related Grants](#)

[Grant/Contract Attachments](#)

The research involves use of Department of Defense (DoD) funding, military personnel, DoD facilities, or other DoD resources. (See [DoD SOP](#) and [DoD Summary](#) for details)

Yes  No

Using the "attachments" button (below), attach applicable materials addressing the specific processes described in the DoD SOP.

[DOD SOP Attachments](#)

Additional Certification: (If your project is federally funded, your funding agency may request an Assurance/ Certification/Declaration of Exemption form.) Check the following if needed:

Protection of Human Subjects Assurance/Certification/Declaration of Exemption (Formerly Optional Form – 310)

Assurance/Certification Attachments

## OTHER REVIEW COMMITTEES

0 unresolved  
comment(s)

If you check any of the below committees, additional materials may be required with your application submission.

Does your research fall under the purview of any of the other review committees listed below? [If yes, check all that apply and attach applicable materials using the attachment button at the bottom of your screen.]

Yes  No

**Additional Information**

Institutional Biosafety Committee

Radiation Safety Committee

Radioactive Drug Research Committee

Markey Cancer Center (MCC) Protocol Review and Monitoring Committee (PRMC)

Graduate Medical Education Committee (GME)

Office of Medical Education (OME)

- [Institutional Biosafety Committee \(IBC\)](#) - Attach required IBC materials
- [Radiation Safety Committee \(RSC\)](#) - For applicability, see instructions and attach form
- [Radioactive Drug Research Committee \(RDRC\)](#)
- [Markey Cancer Center \(MCC\) Protocol Review and Monitoring Committee \(PRMC\)\\*\\*](#) - Attach MCC PRMC materials, if any, per instructions.
- [Office of Medical Education \(OME\)](#)
- [Graduate Medical Education Committee \(GME\)](#)

[Attachments](#)

**\*\* If your study involves cancer research, be sure to select "Cancer Research" in the "Research Attributes" section.** ORI will send your research protocol to the Markey Cancer Center (MCC) Protocol Review and Monitoring Committee (PRMC). The [MCC PRMC](#) is responsible for determining whether the study meets the National Cancer Institute (NCI) definition of a clinical trial and for issuing documentation to you (the investigator) which confirms either that PRMC approval has been obtained or that PRMC review is not required. Your IRB application will be processed and reviewed independently from the PRMC review.

**ADDITIONAL INFORMATION/MATERIALS****0 unresolved  
comment(s)**

Do you want specific information inserted into your approval letter?  Yes  No

Approval Letter Details:

If you wish to have specific language included in your approval letter (e.g., serial #, internal tracking identifier, etc...), type that language in the box below exactly as it should appear in the letter. The text you enter will automatically appear at the top of all approval letters, identical to how you typed it, until you update it. Don't include instructions or questions to ORI staff as those will appear in your approval letter. **If these details need to be changed for any reason, you are responsible for updating the content of this field.**

**Additional Materials:**

If you have other materials you would like to include for the IRB's consideration, check all that apply and attach the corresponding documents using the Attachments button below.

- Detailed protocol
- Dept. of Health & Human Services (DHHS) approved protocol (such as NIH sponsored Cooperative Group Clinical Trial)
- Other Documents

**Protocol/Other Attachments**

Attach Type	File Name
Other	CR Comp AE_SAE listing.pdf

**NOTE: Instructions for Dept. of Health & Human Services (DHHS)-approved protocol**

If you have password protected documents, that feature should be disabled prior to uploading to ensure access for IRB review.

To view the materials currently attached to your application, click "All Attachments" on the left menu bar.

\*You will be able to "sign" your assurance after you have sent your application for signatures (use Submission section). Please notify the personnel required for signing your IRB application after sending for signatures. Once all signatures have been recorded, you will need to return to this section to submit your application to ORI.

**SUBMISSION INFORMATION****0 unresolved  
comment(s)**

Each Section/Subsection in the menu on the left must have a checkmark beside it (except this Submission section) indicating the Section/Subsection has been completed. Otherwise your submission for IRB review and approval cannot be sent to the Office of Research Integrity/IRB.

If applicable, remember to update the Approval Letter Details text box under the Additional Information section

If your materials require review at a convened IRB meeting which you will be asked to attend, it will be scheduled on the next available agenda and you will receive a message to notify you of the date.

If you are making a change to an attachment, you need to delete the attachment, upload a highlighted version that contains the changes (use Document Type of "Highlighted Changes"), and a version that contains the changes without any highlights (use the appropriate Document Type for the item(s)). Do **not** delete approved attachments that are still in use.

Your protocol has been submitted.

## **Statistical Analysis Plan NCT03725332**

To begin, continuous variables (gestational age at birth, neonatal weight, infant hospitalization length of stay, etc.) will be summarized with descriptive statistics (n, mean, standard error, first and third quartiles, and minimum and maximum); categorical variables (NAS treatment required, mother-infant dyad status, preterm birth, maternal smoking status, etc.) will be summarized with counts and percentages. To investigate differences in outcomes between treatment arms, a generalized linear mixed model will be performed. Mixed models allow for additional flexibility to control clustering while controlling for covariates such as socioeconomic status, race, age, addiction severity, if needed. Results will be presented with means (standard error) by treatment arm. Note that the primary outcome requires a noninferiority analysis; the secondary outcomes require superiority analysis to identify between-group differences. Mixed model assumptions will be assessed using plots of each outcome, diagnostics, and/or residual plots. If deviations from distributional assumptions are identified, remedial measures will be deployed as needed. In the case that methods assumptions are not satisfied, remedial measures (eg, variable transformations, nonparametric methods) will be employed.

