**Study Design**

Describe and explain the study design (e.g., observational, secondary analysis, single/double blind, parallel, crossover, deception, etc.).

- *Clinical Research:* Indicate whether subjects will be randomized and whether subjects will receive any placebo.
- *Community-Based Participatory Research:* If you are conducting [community-based participatory research \(CBPR\)](#), describe strategies for involvement of community members in the design and implementation of the study, and dissemination of results from the study.
- *Qualitative research:* Indicate ranges where flexibility is needed, if a fixed interview transcript is not available, describe interview topics including the most sensitive potential questions.
- *Research Repositories:* If the purpose of this submission is to establish a Research Repository (bank, registry) and the material you plan to collect is already available from a commercial supplier, clinical lab, or established IRB approved research repository, provide scientific justification for establishing an additional repository collecting duplicate material. Describe the repository design and operating procedures. For relevant information to include, see the [UK Research Biospecimen Bank Guidance](#) or the [UK Research Registry Guidance](#).

We will perform a stratified cluster randomized controlled trial with randomization of participating clusters into a "GROUP CARE" or "TELEMEDICINE" arm. Sites will be stratified into "high volume" (>500 deliveries/year) and "low volume" (<500 deliveries/year). Randomization will be 1:1 within each strata. According to 2016 site specific delivery data, 6 sites are "low volume" and 6 sites are "high volume". All enrolled study patients will continue to receive regular prenatal care (PNC) through their community based obstetric

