#### Attachments

#### Subject Recruitment Methods & Advertising

Describe how the study team will identify and recruit subjects. Please consider the following items and provide additional information as needed so that the IRB can follow each step of the recruitment process.

- How will the study team identify potential participants?
- Who will first contact the potential subjects, and how?
- Will you use advertisements? If so, how will you distribute those?
- How and where will the research team meet with potential participants?
- If applicable, describe proposed outreach programs for recruiting women, minorities, or disparate populations.
- How you will minimize undue influence in recruitment?
- Attach copies of all recruiting and advertising materials (emails, verbal scripts, flyers, posts, messages, etc.).

For additional information on recruiting and advertising:

- [IRB Application Instructions - Advertisements](#)
- [PI Guide to Identification and Recruitment of Human Subjects for Research](#)

Participants will be recruited based on the following inclusion criteria: Pregnant women at 6-32 weeks gestational age; History of OUD; Who are receiving MAT and obtaining prenatal care at one of the 12 study sites. Patients will be identified by site research nurse (to be determined), viable pregnancy by ultrasound report will be confirmed and diagnosis of OUD and taking MAT will be confirmed. Patient will then be approached about possible recruitment in study. Each study site will have a contracted study nurse who will be identified, CITI trained and added to the IRB for patient recruitment. Although, not an inclusion or exclusion criteria, we have noted that a substantial proportion of potential study participants are under some type of criminal justice supervision at some point during their study participation. We have added a question to the study screener. Importantly, we will not screen or enroll women who are incarcerated in a detention center, easily identified by clothing worn by inmates and/or under escort or restrained by a guard or handcuffs.

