## Research Procedures

Describe how the research will be conducted.

- What experience will study participants have?
- What will study participants be expected to do?
- How long will the study last?
- Outline the schedule and timing of study procedures.
- Provide visit-by-visit listing of all procedures that will take place.
- Identify all procedures that will be carried out with each group of participants.
- Describe deception and debrief procedures if deception is involved.

Differentiate between procedures that involve standard/routine clinical care and those that will be performed specifically for this research project. List medications that are explicitly forbidden or permitted during study participation.

Local staff at each of the 11 sites will be trained as Perinatal Nurse Facilitators, with local residents being trained as peer support specialists. All study participants will receive regular prenatal care through their community based obstetric providers and medication assisted treatment (MAT) with buprenorphine or methadone for opioid use disorder through their respective licensed prescribing providers. In addition to PNC and MAT, study patients will receive a rotating supplementary patient education curriculum (see below) based on the PATHways intervention for OUD in pregnancy. The method by which this will be delivered is based on their allocation into the "group" or "telemedicine" arm of the trial. Half of the participating clusters will be randomized to receive the patient education curriculum through a local group care model imparted through a perinatal nurse facilitator and community based peer support specialist. The remaining clusters will receive the augmented clinical care through telemedicine provided by a Perinatal nurse educator, substance abuse counselor and/or Peer Support Specialists. The research and intervention procedures are identical for participants regardless of their criminal justice status.

Potential perinatal nurse facilitators will be identified at each study site randomized to the "group" arm. These individuals will undergo a two day training program with the UK-PATHways: Hub Perinatal Nurse Facilitator ([name] - see key personnel). [name] will serve as a point person for study site Nurse Facilitators and lead monthly meetings via skype or in person. Peer support specialists will be identified within the region (3 total), and, if not previously certified/trained, training will be provided.

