14. Anxiety: GAD7 administered at intake, 3rd trimester, 3 and 6 months postpartum
15. Quality of life: WHO QoL-BRF administered in 3rd trimester, 3 and 6 months post-partum
16. Mother-Infant dyad status/Foster care requirement: retention of custody evaluated by patient interview at hospital discharge, 3 and 6 months postpartum
17. Maternal breastfeeding status: evaluated by patient interview at delivery, 3 and 6 months postpartum.

We will be collecting the following fetal data:

Fetal size per gestational age; Any genetic or structural anomalies; any other fetal complications.

We will be collecting the following neonatal data, including the following assessments:

Gestational age and weight at birth; 5 & 10min Apgar score; NICU/nursery hospital admission; NAS diagnosis & treatment requirement (primary outcome); NAS medication days; in-hospital growth (birth to discharge per day); other infant morbidities; total hospitalization length of stay; immunization compliance, ED visits, follow up with scheduled pediatric visits.

Data will be obtained via medical record review, patient interview, physician/staff report, review of state Medicaid data, and hospital discharge data by the study site research staff with the oversight of the UK-study team.

We will perform fidelity monitoring of intervention delivery. Research nurses/facilitators (group arm), providers (telemedicine arm), and all study participants will be asked to complete a fidelity form, similar to an evaluation form, at the end of each educational session. We will evaluate intervention fidelity by comparing provider and participant responses. If any discordance is identified between provider and participant responses for a given topic, additional training related to intervention delivery may be required.

In each arm, patients will be randomly selected to participant in a qualitative interview process at each participating site at the time of the 6 month postpartum follow-up. The interviews will be facilitated by Co-I [name], who has extensive experience using qualitative techniques with substance-involved patients in community based and treatment settings, with the assistance of research coordinators trained in qualitative interviewing techniques. Patients will be offered a fifty dollar stipend for their time to participate in the interview. 3 patients will be randomly selected from each participating site for a total of 33 interviews.

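### The SAP's mixed model names neither the delivery-volume stratum used to randomise sites nor an inference method suited to 11 or 12 sites, so its error bars can be wrong in either direction

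*Combined protocol and SAP*

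**What the plan says.** Under Study Design, whole sites are randomised after stratification by annual deliveries (above or below 500), with 6 low-volume and 6 high-volume sites: "Randomization will be 1:1 within each strata". That implies 3 against 3 in each stratum.

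The SAP is one paragraph. Its analysis sentence is "To investigate differences in outcomes between treatment arms, a generalized linear mixed model will be performed". The model is said to handle clustering while "controlling for covariates such as socioeconomic status, race, age, addiction severity, if needed". These are all patient-level variables, the list is open, and delivery volume is not on it. On the hypotheses it says "Note that the primary outcome requires a noninferiority analysis; the secondary outcomes require superiority analysis to identify between-group differences". If assumptions fail, "remedial measures (eg, variable transformations, nonparametric methods) will be employed"; the unit for those methods (site or mother) is not stated. No estimation method, reference distribution, degrees of freedom, alpha, sidedness, effect scale or margin is given.

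The number of sites differs between sections. Subject Demographics lists 12, Study Design gives 6 + 6, and the recruitment section has "obtaining prenatal care at one of the 12 study sites". Research Procedures has "Local staff at each of the 11 sites will be trained as Perinatal Nurse Facilitators", Resources also gives 11, and the interview plan reads "3 patients will be randomly selected from each participating site for a total of 33 interviews" (33 / 3 = 11).

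**The concern.** Arm is a site-level factor, so the precision of the GROUP versus TELEMEDICINE comparison depends on the number of sites as well as the number of mothers. Two choices then matter, and the SAP settles neither.

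- **Reference distribution.** With 11 or 12 sites, a normal (z) reference understates the uncertainty once sites truly differ. The test becomes too liberal, which in a noninferiority trial means declaring noninferiority too often.
- **Stratum.** Stratified allocation balances delivery volume across arms. If volume predicts NAS and is left out of the model, its effect is counted as random variation between sites. The standard error is then too large, the test conservative, and power is lost.

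Analyses that all comply with the SAP can therefore have quite different error rates, and the noninferiority conclusion could turn on a choice made after the data are seen.

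**Working it through.** The plan states no error rate, power or sample-size calculation, so there is no figure of its own to reproduce.

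**From the documents:** 12 or 11 sites; two strata, allocated 1:1; a maximum of 267 subjects (taken as mothers), or 267 / 12 = 22.25 per site.

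**Assumed:** one-sided 2.5%; latent-scale ICC 0.01, 0.05 or 0.10; reference NAS rate 40%; margin odds ratio 1.5; stratum log-odds difference 0 or 1.0; high-volume sites enrolling twice as many mothers as low-volume sites.

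**Step 1: degrees of freedom.** Intercept, arm and stratum use three parameters at site level: 12 - 3 = 9, or 11 - 3 = 8.

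- t(0.975) is 2.262 on 9 df and 2.306 on 8 df, against z = 1.960.
- Interval widening: 2.262 / 1.960 = 1.154 and 2.306 / 1.960 = 1.177, or about 15% and 18%.
- Using z where t is correct turns 2.5% into P(t > 1.96) = 4.1% (9 df) or 4.3% (8 df). This is exact only for a normal outcome analysed by site means. It is a benchmark, not the error of the SAP's model.

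**Step 2: why omitting the stratum is conservative.** On the log-odds scale, with equal sites:

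- Site variance = ICC / (1 - ICC) x pi^2 / 3 = 0.033, 0.173, 0.366 at ICC 0.01, 0.05, 0.10.
- Binomial variance per site is about 1 / (22.25 x 0.4 x 0.6) = 0.187.
- An omitted stratum difference of 1.0 (coded as plus or minus 0.5) adds 0.5^2 = 0.25.
- Standard-error inflation: sqrt(0.470 / 0.220) = 1.46, sqrt(0.610 / 0.360) = 1.30, sqrt(0.803 / 0.553) = 1.21.

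The effect is largest when sites otherwise differ little.

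**Step 3: simulated noninferiority error of the SAP's model class.** Random-intercept logistic model, maximum likelihood, Wald test at the margin, 1,500 trials per row (Monte Carlo SE about 0.4 points at 2.5%), nominal 2.5%:

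| Sites | ICC | Stratum log-odds | No stratum, z | Stratum, z | Stratum, t (sites - 3) |
|---|---|---|---|---|---|
| 12 | 0.01 | 0 | 2.5% | 2.7% | 1.1% |
| 12 | 0.01 | 1.0 | 0.7% | 2.9% | 1.1% |
| 12 | 0.05 | 0 | 4.3% | 5.1% | 2.8% |
| 12 | 0.05 | 1.0 | 1.9% | 4.7% | 2.9% |
| 12 | 0.10 | 0 | 4.7% | 5.3% | 3.5% |
| 12 | 0.10 | 1.0 | 2.8% | 5.9% | 4.0% |
| 11 | 0.01 | 0 | 3.1% | 3.3% | 1.8% |
| 11 | 0.01 | 1.0 | 0.9% | 2.3% | 1.0% |
| 11 | 0.05 | 0 | 4.3% | 4.6% | 2.9% |
| 11 | 0.05 | 1.0 | 3.0% | 6.2% | 3.6% |
| 11 | 0.10 | 0 | 5.3% | 6.0% | 3.3% |

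The setting with 11 sites, ICC 0.10 and stratum effect 1.0 was not completed.

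**Step 4: other assumptions.**

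- 12 sites, 267 mothers, NAS 50%, 10-point risk-difference margin, no stratum, z. At ICC 0.01 / 0.02 / 0.05 / 0.10, error is 3.4 / 3.9 / 5.0 / 5.0% if volume is not prognostic and 0.6 / 1.0 / 1.6 / 2.3% at stratum log-odds ratio 1.0.
- A balanced normal outcome (12 sites of 22, REML) gives about 2.6 to 4.1% with the stratum and z, and about 0.9 to 2.2% with a prognostic stratum omitted.

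**Step 5: noninferiority power** (arms equal, 12 sites, 267 mothers, ICC 0.02, assumed 20-point margin):

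| Stratum log-odds ratio | Mixed model, no stratum, z | Mixed model, stratum, t9 | Site-level regression, t9 |
|---|---|---|---|
| 0 | 86% | 80% | 70% |
| 0.6 | 79% | 81% | 72% |
| 0.85 | 71% | 81% | 72% |
| 1.0 | 65% | 82% | 74% |

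**The case against.** The strongest reply is that a mixed model already accounts for clustering, that the open covariate list lets the analyst add the stratum, and that the SAP never prescribes a z reference. All of that is true. A reader might infer that the SAP rules the stratum out or mandates large-sample inference; it does neither. What remains is that both choices are left open when few sites make them matter.

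A second reply is that the two effects offset each other. They can: with NAS 50%, ICC 0.10 and stratum log-odds ratio 1.0, the no-stratum z analysis gives 2.3%. A reader might therefore infer from the few sites alone that the error rate is inflated. The documents do not support that, since the net direction depends on quantities they do not give. Nor do they support relying on the offset.

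Third, the missing alpha and margin leave the test undefined whatever is done about stratum and degrees of freedom. That stands. These two gaps are not the sole reason the error rate is undetermined, but supplying alpha and margin would not close them.

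Fourth, a reader might infer that the mixed model should give way to a site-level analysis, whose simulated error stays at about 2.2 to 2.6%. That is a trade-off, not a correction. In Step 5 it has 8 to 10 points less power than the mixed model with stratum and t, and an unweighted version targets an average over sites instead of over mothers.

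**Conclusion.** The concern holds: the stratum and a small-sample reference are not prespecified, and the resulting error bars can be too narrow or too wide. With 267 mothers and an assumed one-sided 2.5%, z with the stratum reaches about 4 to 6% as the ICC rises to 0.10. Omitting a strongly prognostic stratum can bring error to about 1% or below at low ICC, and in Step 5 costs up to 82 - 65 = 17 points of power against the model with stratum and t.

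The omissions and the 9 or 8 degrees of freedom come from the documents. Every simulated size rests on the assumed alpha, margin, NAS rate, ICC and stratum effect; no document links delivery volume to NAS.

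The point covers only the randomised GROUP versus TELEMEDICINE comparison. A reader might extend it to Aim 2, which sets each arm against the UK-PATHways hub. The hub is a single non-randomised programme, so this site-count argument does not carry over. It should be fixed before outcome data are analysed.

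**What to change.** Keep the generalized linear mixed model as the primary analysis and state in the SAP:

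- Delivery-volume stratum is a fixed effect and site a random intercept.
- The arm comparison uses a t reference with (number of analysed sites minus 3) degrees of freedom. The count must be of analysed sites, because a site contributing no data adds no information.
- Secondary outcomes use the same model terms and degrees of freedom.
- Any nonparametric fallback is done at site level or by permutation within strata.
- A regression of site results on arm and stratum, with the same t reference and its weighting fixed in advance, is a sensitivity analysis.
- Alpha, sidedness, effect scale and noninferiority margin are given.

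Reconcile the 12-site sections (Subject Demographics, Study Design, recruitment) with the 11-site sections (Research Procedures, Resources, interview plan). The degrees of freedom follow from the count, and 11 sites cannot be split evenly in both strata.

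Cost: SAP wording and a few lines of code. Intervals widen by about 15% (9 df) or 18% (8 df), and one degree of freedom goes to the stratum. If volume is not prognostic, power in Step 5 falls from 86% to 80%. The corrected model remains approximate: 1.0 to 4.0% in Step 3, and up to 4.6% in a wider set of assumptions, half of which used 533 mothers (15 + 15 + 503, the planned-enrolment rows summed) instead of the stated maximum of 267.
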